6.5 Statistical Analyses

6.5.1 Primary endpoint analysis

The primary endpoints, including incidence of sustained ventricular tachycardia (1~6 Month Post-operation) and newly formed tumors (12 Month Post-operation) will be analyzed using descriptive statistics (number of observations, mean, median, standard deviation, minimum, and maximum) for continuous variables and using frequencies and percentages for categorical and ordinal variables. A final analysis will be conducted when all subjects have completed the study participation.

6.5.2 Secondary endpoint analysis

Secondary endpoints were analyzed using descriptive statistics. The comparative assessment of treatment effects employed distinct analytical approaches based on variable characteristics. Continuous variables are presented with mean, standard deviation, median, maximum and minimum values, and range, compared using the t-test method. Categorical and ordinal data are reported as frequencies (percentages), compared using the Wilcoxon rank-sum test. A two-sided p-value of ≤ 0.05 was considered statistically significant for all analyses.

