	 Incidence of perioperative serious adverse events (SAEs): Such as Mortality, Non-fatal myocardial infarction, Stroke, Cardiac perforation, Cardiac tamponade, etc. Allogeneic immune monitoring: PRA, DSA (2 week, 1, 3, 6 and 12 Month Post-operation) 					
	3. Perioperative cardiac monitoring: (1 Month Post-operation)					
	Efficacy:					
	Left ventricular function assessment:					
	2. Six-minute walk test: o Distance walked measured at 6 and 12 months postoperatively.					
	3. NYHA functional classification: • Assessed at 6, and 12 months postoperatively.					
	 4. Quality of life evaluation: Minnesota Living with Heart Failure Questionnaire (MLHFQ) administered at 6, and 12 months postoperatively. 					
	5. Major adverse cardiac events (MACE) incidence: o Mortality; Non-fatal myocardial infarction; Heart failure-related rehospitalization					
Statistical Methods and Data Analyses	The trial results will be analyzed primarily using descriptive statistics.					

	Continuous variables will be presented as mean ± standard deviation, along with median, minimum, and maximum values. 95% confidence intervals for means will be estimated using the t-distribution method. Between-group comparisons of means will be performed using Student's t-test. Categorical and ordinal data will be summarized as frequencies (percentages) and rates. 95% confidence intervals for rates will be calculated using the Miettinen method. Between-group comparisons of proportions will be conducted using Fisher's exact test. Longitudinal comparisons (e.g., PRA, DSA, 6-minute walk distance, NYHA functional class, MLHFQ scores) will be analyzed using repeated measures ANOVA to assess dynamic changes over time.
Duration	2 years

.

LIST OF ABBREVIATIONS

iPSC	Induced pluripotent stem cells
HF	Heart failure
CABG	Coronary artery bypass graft
ICD	Implantable cardioverter defibrillator
LVEF	Left ventricular ejection fraction
LVEDV	Left ventricular end-diastolic volume
LVESV	Left ventricular end-systolic volume
MRI	Magnetic resonance imaging
CT	Computed tomography
cTnI	Cardiac troponin I
cTnT	Cardiac troponin T
CKMB	Creatine phosphokinase-Mb
NT-proBNP	N-terminalpro-brain natriuretic peptide
PCT	Procalcitonin
TSH	Thyroid stimulating hormone
ECG	Electrocardiogram
NYHA	New York Heart Association
MACE	Major adverse cardiac events
MLHFQ	Minnesota Quality of Life Questionnaire for Heart Failure
6MWD	6min walking test distance
PCI	Percutaneous coronary intervention
HLA	Human leukocyte antigen

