2.2.2 Secondary endpoints

Efficacy:

- 1. Cardiac MRI Assessment of Left Ventricular Function:
 - o Comparative analysis of baseline versus postoperative measurements at 6, and 12 months, including: Infarcted size; End-diastolic lateral wall thickness; Focal septal thickness; Ejection fraction; End-diastolic volume; End-systolic volume; Stroke volume; Cardiac output; Myocardial density; End-diastolic myocardial mass
- 2. Echocardiographic Evaluation of Left Ventricular Function:
 - o Comparative analysis of baseline versus postoperative measurements at 6, and 12 months, including: End-diastolic septal thickness; Left ventricular end-diastolic

diameter; Left ventricular end-systolic diameter; Left ventricular posterior wall thickness at end-diastole; Left atrial diameter; Left ventricular ejection fraction; Mitral inflow velocity profile (E/A ratio)

- 3. Myocardial Perfusion Imaging (PET/ECT):
 - o Comparative analysis of left ventricular perfusion at preoperative, 6-month, and 12-month postoperatively
- 4. Six-Minute Walk Test (baseline, 6 and 12 months)
- 5. NYHA Functional Classification (baseline, 6 and 12 months)
- 6. Minnesota Living with Heart Failure Questionnaire (MLHFQ) (baseline, 6 and 12 months)
- 7. Incidence of Major Adverse Cardiac Events (MACE) including: Mortality; Non-fatal myocardial infarction; Heart failure rehospitalization

Safety:

- 1. Incidence of Perioperative Serious Adverse Events (SAE) Incidence: Mortality; Nonfatal myocardial infarction; stroke; cardiac perforation; cardiac temponade, etc.
- 2. Alloimmune Response Monitoring (PRA, DSA): (baseline, 1, 6 and 12 months)
- 3. Perioperative Electrocardiographic Monitoring (Within 1 month postoperatively)
- 4. Laboratory Tests, including Complete blood count, Comprehensive metabolic panel; NT-proBNP;Troponin; Myocardial enzyme profile; Procalcitonin; Immunological panel (C3, C4, IgA, IgG, IgM); Coagulation profile, etc.

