3.2 Exclusion Criteria

- 1. PRA \geq 20% or DSA-positive.
- 2. Previous implantation of ICD, CRT or similar treatment.
- 3. Valvular heart disease or received heart valvular disease
- 4. Previous percutaneous transluminal coronary intervention (PCI)
- 5. Atrial fibrillation
- 6. History of sustained ventricular tachycardia or sudden cardiac death.
- 7. Baseline glomerular filtration rate <30ml/min/1.73m2.
- 8. Liver dysfunction, as evidenced by enzymes (AST and ALT) greater than three times the ULN.
- 9. Hematological abnormality: A hematocrit <25% as determined by HCT, white blood cell<2500/ul or platelet values <100000/ul without another explanation.
- 10. Known, serious radiographic contrast allergy, penicillin allergy, streptomycin allergy.

Protocol (version 6.1)

Version data: 2021.08.01

Confidential
Page 18 of 38

- 11. Coagulopathy (INR>1.3) not due to a reversible cause.
- 12. Contra-indication to performance of an MRI scan.
- 13. History of organ transplant.
- 14. Clinical history of malignancy within 5 years (patients with prior malignancy must be disease-free for 5 years).
- 15. Non-cardiac condition that limits lifespan <1 year.
- 16. Chronic therapy with immunosuppressant medication, such as glucocorticoids and TNF α antagonist.
- 17. Patients' allergy to or contra-indication to immunosuppressants.
- 18. Serum positivity for HIV, HBV, HCV, TP.
- 19. Currently enrolled in other investigational therapeutic or device study.
- 20. Female patient who is pregnant or breast-feeding.
- 21. Other conditions that researchers consider not suitable to participate in this study.

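### Continuous secondary endpoints are compared by a t-test without baseline adjustment, although baselines are collected and there are 10 patients per arm; the synopsis also puts NYHA class and DSA under repeated-measures ANOVA, which section 6.5.2 does not mention

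*Protocol*

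**What the plan says.** **Method in the body.** Protocol section 6.5.2 states for continuous data: "Continuous variables are presented with mean, standard deviation, median, maximum and minimum values, and range, compared using the t-test method". For the rest it states: "Categorical and ordinal data are reported as frequencies (percentages), compared using the Wilcoxon rank-sum test". It does not mention repeated-measures ANOVA.

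**Method in the synopsis.** Under Statistical Methods and Data Analyses: "Between-group comparisons of means will be performed using Student's t-test". Fisher's exact test is named there for proportions. The same paragraph adds: "Longitudinal comparisons (e.g., PRA, DSA, 6-minute walk distance, NYHA functional class, MLHFQ scores) will be analyzed using repeated measures ANOVA". Walk distance and MLHFQ therefore fall under two methods in the synopsis, and NYHA class falls under ANOVA there but under the Wilcoxon test in 6.5.2.

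**Baselines.** Section 2.2.2 frames the MRI and echocardiography endpoints as "Comparative analysis of baseline versus postoperative measurements at 6, and 12 months" and lists baseline, 6 and 12 months for walk test, NYHA and MLHFQ. Perfusion imaging has a preoperative measurement. Table 3 schedules all of these at baseline.

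**Design.** Sections 6.3 and 6.4 give 10 patients per arm from a 1:1 list of 20 codes. No stratification is stated.

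**DSA.** Section 3.2 excludes patients with PRA at or above its threshold "or DSA-positive". No section gives the scale on which the DSA endpoint is recorded.

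**The concern.** The efficacy question is whether cells add anything to CABG, and all the efficacy evidence comes from these secondary endpoints in 20 patients. In a sample this small, chance differences at baseline are common. An unadjusted comparison of follow-up values passes part of such a difference into the result, and so does a comparison of changes, in the opposite direction. Because the protocol does not say which of the two is meant, two analysts could follow it and report different estimates from the same data.

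The ANOVA list is a separate defect. NYHA class is ordinal, so a method that compares means does not suit it, and the two parts of the protocol disagree on its test. If DSA is recorded as positive or negative, as the entry criterion uses it, every baseline is negative, and a baseline level without variance does not fit the ANOVA model.

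**Working it through.** **The plan's own figure.** The sample size of 20 comes without effect size, SD or power. It can be neither reproduced nor called wrong. The check below concerns precision only.

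**Inputs.** n = 10 per arm (section 6.3); two-sided alpha 0.05 (section 6.5.2). The baseline-to-follow-up correlation r is not in the documents; it is an assumption, taken over 0.3 to 0.8. SDs are assumed equal at baseline and follow-up, and differences are in SD units.

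**Chance imbalance.** The SD of the difference in baseline means is sqrt(2/10) = 0.447. P(gap > 0.5 SD) = 2[1 − Φ(0.5/0.447)] = 2[1 − Φ(1.118)] = 0.264. For a gap above 1 SD the probability is 0.025.

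**Variance of the between-arm difference.**
- Follow-up t-test: 2/n
- Change-score t-test: 2(1 − r) × 2/n
- ANCOVA: (1 − r²) × (2/n) × [1 + 1/(2n − 4)]

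The last factor is the cost of estimating the slope: 1 + 1/16 = 1.0625. At r = 0.5 the ratio of ANCOVA to follow-up is 0.75 × 1.0625 = 0.80. At r = 0.7 it is 0.51 × 1.0625 = 0.54. Against change at r = 0.7 it is 0.542/0.60 = 0.90.

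| r | ANCOVA / follow-up | ANCOVA / change | Power for 1 SD: follow-up, change, ANCOVA |
|---|---|---|---|
| 0.3 | 0.97 | 0.69 | 56%, 43%, 57% |
| 0.5 | 0.80 | 0.80 | 56%, 56%, 66% |
| 0.7 | 0.54 | 0.90 | 56%, 78%, 82% |
| 0.8 | 0.38 | 0.96 | 56%, 92%, 93% |

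Power is from the noncentral t distribution, with 18 df for the t-tests and 17 for ANCOVA.

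**Equivalent sample size.** To match ANCOVA, a follow-up t-test needs 10/0.797 = 12.5 per arm at r = 0.5 and 10/0.542 = 18.5 at r = 0.7. A change-score t-test needs 12.5 and 11.1.

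**Where the gain ends.** Against follow-up values, ANCOVA stops helping when (1 − r²) × 1.0625 = 1, that is r ≈ 0.24. Against change scores it stops when (1 + r)/2 × 1.0625 = 1, that is r ≈ 0.88.

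**What a 0.5 SD gap does.** The follow-up comparison shifts by 0.5r, which is 0.15 to 0.40 SD for r from 0.3 to 0.8. The change comparison shifts by 0.5(1 − r) the other way, which is 0.35 to 0.10 SD. ANCOVA removes the shift.

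**Validity.** In 40,000 simulated trials per setting, type I error over all randomisations was about 5% for all three methods.

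**The case against.** The strongest reply is that nothing here is invalid. Randomisation makes the unadjusted between-arm t-test unbiased on average, and its error rate is correct. The trial is exploratory, claims no power and is to be analysed mainly descriptively. If the t-test is meant for changes, as the wording of the imaging endpoints suggests, the baseline is already partly used. ANCOVA then gains only 10% in variance at r = 0.7 and 4% at r = 0.8. The entry range for LVEF (20 to 45%) may also narrow baseline spread and lower the correlation. All of this stands, and it limits the size of the point.

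A reader might go further in four ways that the documents do not support:
- That the ANOVA will be read through its group main effect, which averages in the pre-treatment visit. No section specifies that effect; the stated aim, "will be analyzed using repeated measures ANOVA to assess dynamic changes over time", fits time or group-by-time effects at least as well.
- That a patient who misses a visit will be dropped. The protocol does not say so, and handling of missing data is commonly left to the analysis plan.
- That within-arm change will serve as evidence of efficacy although both arms have CABG. Section 2.2.2 lists measurements and visits, while the synopsis specifies comparisons between groups.
- That DSA is certainly binary. This is inferred from the exclusion criterion alone.

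Suitable tests for NYHA (Wilcoxon) and for proportions (Fisher) are already in the protocol, so for these two variables the defect lies in the synopsis list.

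**Conclusion.** The point holds as one of efficiency and clarity. The protocol names an unadjusted t-test, leaves open what it is applied to, and forgoes a nearly free gain in precision. For an assumed correlation of 0.5 to 0.7, variance falls by about 20 to 46% against follow-up values (worth 12.5 to 18.5 per arm instead of 10) and by about 20 to 10% against changes. The gain over follow-up values is about 3% at 0.3 and nil below about 0.24. These sizes rest on the assumed correlation and equal SDs. The 26% chance of a gap above 0.5 SD needs no correlation and applies to each endpoint taken singly.

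It would be too strong to say that the t-test is invalid, or that only an adjusted contrast answers the question. The loss lies in precision and in an estimate that carries part of the imbalance observed.

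The conflict over NYHA between the synopsis and section 6.5.2 is plain on the text. The DSA part depends on how DSA is recorded. The primary safety endpoints are unaffected.

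**What to change.** 1. For continuous efficacy endpoints, replace the t-test and the repeated-measures ANOVA, in both section 6.5.2 and the synopsis, by a baseline-adjusted between-arm comparison. This can be ANCOVA of the 12-month value on arm and baseline, or a mixed model of the 6- and 12-month values with baseline as covariate. Report the adjusted difference with its 95% CI. This also settles whether follow-up or change is tested.
2. Remove NYHA class and DSA from the ANOVA list in the synopsis. Analyse NYHA by the Wilcoxon test already in 6.5.2.
3. State the scale of DSA. If it is positive/negative, use the Fisher's exact test already in the synopsis, and align 6.5.2, which now assigns the Wilcoxon test to categorical data as well.

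The cost is wording, one degree of freedom per model and a small loss of precision if the correlation is low: at r = 0.2 the variance is 0.96 × 1.0625 = 1.02 times that of the follow-up t-test. No new data, visits or patients are needed.

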6.3 Sample Size Determination

This is an exploratory study. The total sample size is 20, with 10 allocated to the cell therapy group and 10 to the control group

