6.4 Randomization and blinding

The trial employed an open-label design with single-blind outcome assessment. To mitigate evaluation bias, Assessors assessing treatment efficacy were blinded to group assignments.

Prior to trial initiation, a statistician generated 20 randomization codes using SAS PLAN procedure with 1:1 allocation. Sequentially numbered (1-20), opaque sealed envelopes containing group assignments were prepared, each bearing its corresponding identification number. Following written informed consent and successful screening, the designated envelope was opened immediately before surgery to reveal group allocation and initiate the assigned procedure. This ensured allocation concealment during screening and prerandomization phases, preventing selection bias.

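### The t-test fixed for continuous efficacy endpoints does not condition on the baseline values the trial collects, which costs precision in a 20-patient trial

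*Protocol*

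**What the plan says.** **Between-arm method.** Section 6.5.2: "Continuous variables are presented with mean, standard deviation, median, maximum and minimum values, and range, compared using the t-test method". The synopsis (Statistical Methods and Data Analyses): "Between-group comparisons of means will be performed using Student's t-test". No covariate is named in either place, and neither says whether the variable tested is the follow-up value or the change from baseline.

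**Longitudinal method, synopsis only.** Longitudinal comparisons "will be analyzed using repeated measures ANOVA to assess dynamic changes over time". The examples given there include six-minute walk distance and MLHFQ score but no imaging endpoint. Section 6.5.2 does not mention this method.

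**Baseline data.** Section 2.2.2 describes the MRI and echocardiography endpoints as "Comparative analysis of baseline versus postoperative measurements at 6, and 12 months". It gives the same three time points for perfusion imaging, six-minute walk and MLHFQ, and Table 3 schedules all of them.

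**Design.** Section 6.3: "The total sample size is 20, with 10 allocated to the cell therapy group and 10 to the control group". Section 6.4: "a statistician generated 20 randomization codes using SAS PLAN procedure with 1:1 allocation", with no stratification factor named. Section 6.5.2 sets the threshold: "A two-sided p-value of ≤ 0.05 was considered statistically significant for all analyses".

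**The concern.** A baseline value of the outcome is usually among its best predictors, and here it is measured for every continuous efficacy endpoint. A t-test on follow-up values ignores it. A t-test on change uses it with the coefficient forced to 1, which over-corrects whenever the baseline-to-follow-up slope is below 1. ANCOVA estimates that coefficient from the data.

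With 10 patients per arm and no stratification, sizeable chance differences at baseline are to be expected, and both t-tests carry part of any such difference into the estimated effect. Efficacy is part of the stated objective, and what an exploratory trial yields on efficacy is an estimate with its uncertainty. Because the protocol itself names the t-test, an analysis plan that used ANCOVA would depart from it.

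**Working it through.** **Inputs from the protocol.** n = 10 per arm (6.3); two-sided 0.05 (6.5.2); baseline and two follow-up values for each measure (2.2.2, Table 3). The sample size of 20 comes with no effect size, SD or power, so there is no figure of the plan's own to reproduce.

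**Assumptions.** r is the baseline-to-follow-up correlation, which the documents do not give, so a range is shown. Normal data, the same SD σ at baseline and follow-up, and no missing values.

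**Step 1: chance imbalance.** The difference in baseline means has SD √(2/10) = 0.447 σ. P(|difference| > 0.5 σ) = 2 × [1 − Φ(0.5/0.447)] = 26%. For 0.75 σ it is 9%.

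**Step 2: shift given an imbalance of 0.5 σ.** The follow-up t-test estimate moves by 0.5r σ. The change-score estimate moves the other way by 0.5(1 − r) σ. At r = 0.5 these are 0.25 and 0.25 σ, at r = 0.6 they are 0.30 and 0.20 σ, and at r = 0.7 they are 0.35 and 0.15 σ. ANCOVA removes the shift in expectation.

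**Step 3: variance of the estimated difference, in units of (2/n)σ².**
- t-test on follow-up: 1
- t-test on change: 2(1 − r)
- ANCOVA: (1 − r²) × [1 + 1/(2n − 4)] = (1 − r²) × 1.0625

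Steps 2 and 3 describe one cost. The follow-up variance splits as 1 = r² + (1 − r²), and the change variance as 2(1 − r) = (1 − r)² + (1 − r²). In each, the first term is the part due to baseline imbalance. At r = 0.6 that part is 0.36 of 1, or 0.16 of 0.80.

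**Step 4: ratio of 95% interval widths.** Critical values are t(17) = 2.1098 for ANCOVA and t(18) = 2.1009 for the t-tests, a ratio of 1.0042. Example at r = 0.6: against follow-up, √(0.64 × 1.0625) × 1.0042 = 0.83; against change, √(0.68/0.80) × 1.0042 = 0.93.

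| r | ANCOVA / follow-up t-test | ANCOVA / change-score t-test |
|---|---|---|
| 0.3 | 0.99 | 0.83 |
| 0.5 | 0.90 | 0.90 |
| 0.6 | 0.83 | 0.93 |
| 0.7 | 0.74 | 0.95 |

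**Step 5: where ANCOVA loses.** Against the follow-up t-test, break-even is at r of about 0.25 (variance: √(1 − 1/1.0625) = 0.24; interval width: 0.26). The worst case, at r = 0, is √1.0625 × 1.0042 = 1.035, or 3.5% wider. Against the change-score t-test, variance breaks even at r = 2/1.0625 − 1 = 0.88, and interval width marginally earlier, at 2/(1.0625 × 1.0042²) − 1 = 0.87. At r = 0.9 ANCOVA is about 1% wider.

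**Step 6: check.** Simulation with 40,000 trials per setting gave type I error between 0.048 and 0.052 for all three methods. At r = 0.5 the empirical SDs of the estimates were 0.446, 0.447 and 0.400 (follow-up, change, ANCOVA), against 0.447, 0.447 and 0.399 from the formulas. For illustration only, power for a 1 SD effect at r = 0.6 from the noncentral t is 56%, 66% and 72%.

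**The case against.** **The t-test is valid.** This stands. Its type I error is about 5% and it is unbiased over repeated randomisation. A reader might infer that the efficacy estimates are biased, or that imbalance is a harm on top of the lost precision. Neither follows: the shift is conditional on the allocation that happens to occur, and its variability is already in the t-test's standard error.

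**The synopsis does name a method that can use baseline.** This stands in part. Repeated measures ANOVA with baseline as a time point could bring baseline in for six-minute walk and MLHFQ, and its list of examples is open-ended. But it is described as assessing change over time, lists no imaging endpoint and is absent from section 6.5.2, so the two places do not give one between-arm method.

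**The t-test may be meant for change scores.** Section 2.2.2's wording for MRI and echocardiography points that way. Over r = 0.5 to 0.7 the gain is then only 5 to 10% in interval width, and the larger gains (down to 0.74) apply only if baseline is ignored altogether.

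**r may be low.** Eligibility restricts LVEF to 20–45%, and every patient has CABG between baseline and follow-up; both could weaken the correlation. At r = 0.3 the gain over the follow-up t-test is 1%. The possible loss is small, however (Step 5).

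**Chance imbalance might be thought to swamp any real effect.** The documents do not support this, since they state no effect size to set it against.

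**Conclusion.** The point holds as an efficiency improvement to secondary endpoints of an exploratory trial that is analysed mainly descriptively. The protocol fixes a between-arm test that does not condition on baseline, leaves open what the test is applied to, and describes the longitudinal analysis in one place only.

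For r between 0.3 and 0.7, ANCOVA narrows the 95% interval by 1 to 26% against a follow-up t-test and by 5 to 17% against a change-score t-test. Its worst loss against the follow-up test is 3.5%, at r = 0. These sizes rest on an assumed r, equal SDs and complete data. ANCOVA also removes the need to choose between the two t-tests, a choice the protocol does not make. Neither primary safety endpoint is affected, and the t-test results would not be invalid.

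**What to change.** In section 6.5.2 and the synopsis, replace the t-test for continuous efficacy endpoints by ANCOVA at month 6 and at month 12, with the follow-up value as outcome and randomised arm and the same measure's baseline as terms. Report the adjusted between-arm difference with its 95% confidence interval. Reword the synopsis's repeated measures ANOVA so that it agrees with this and both places state the same between-arm method.

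The change should not be extended to NYHA class by stratifying on baseline class: entry is limited to classes III and IV, and with 20 patients one stratum could be very small.

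The cost is wording and one residual degree of freedom per model (critical value 2.110 instead of 2.101). No new patients, visits or measurements are needed.

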2.2 Study Endpoints

2.2.1 Primary endpoints

Safety:

- 1. Incidence of sustained ventricular tachycardia (1~6 Month Post-operation)
 - o Defined as the proportion of patients experiencing ventricular tachycardia lasting more than 30 seconds
- 2. Incidence of newly formed tumors (12 Month Post-operation)
 - o By comparing chest, abdominal and pelvic CT scan and PET-CT scan

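### Binary secondary endpoints have two stated tests (Fisher in the synopsis, Wilcoxon rank-sum in 6.5.2) that can disagree at 10 per arm, and 6.5.1 omits the interval for rates that the synopsis promises

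*Protocol*

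**What the plan says.** **Secondary endpoints, section 6.5.2.** "Categorical and ordinal data are reported as frequencies (percentages), compared using the Wilcoxon rank-sum test". The same section sets the threshold: "A two-sided p-value of ≤ 0.05 was considered statistically significant for all analyses". It does not say whether the rank-sum test is exact or asymptotic, and it does not separate yes/no outcomes, ordered scales and unordered categories.

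**Synopsis, statistical methods.** "Between-group comparisons of proportions will be conducted using Fisher's exact test". On intervals: "95% confidence intervals for rates will be calculated using the Miettinen method". It does not say whether these are intervals for a single rate or for a difference between groups.

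**Primary endpoints, sections 2.2.1 and 6.5.1.** Both primary endpoints are incidences. Sustained ventricular tachycardia is "Defined as the proportion of patients experiencing ventricular tachycardia lasting more than 30 seconds". Section 6.5.1 analyses the primary endpoints "using frequencies and percentages for categorical and ordinal variables", with means and medians for continuous variables, although neither primary endpoint is continuous. It mentions no interval and no test.

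**Size, section 6.3.** "The total sample size is 20, with 10 allocated to the cell therapy group and 10 to the control group".

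**The concern.** MACE incidence (section 2.2.2) is a proportion of patients. It is covered by the synopsis rule for proportions and by the 6.5.2 rule for categorical data. Two tests are therefore written down for one comparison, with a significance threshold attached and no order of precedence. If they can fall on opposite sides of that threshold, whoever runs the analysis can settle the result after seeing the data.

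Two lesser points go with this. A rank-sum test has no meaning for unordered categories with more than two levels, and 6.5.2 as worded includes them. The listed secondary endpoints do not clearly contain such a variable, so this is mainly a matter of wording. Also, the main question of the trial is safety in 10 treated patients, and the section that governs the primary analysis does not carry over the interval promised in the synopsis. A reader who follows 6.5.1 alone would report no events in 10 as 0%, with nothing to show how little that excludes.

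**Working it through.** The protocol gives no power, event rate or effect size, so there is no figure of its own to reproduce. The check asks whether the two stated tests can disagree at this sample size.

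**Inputs.** 10 patients per arm (6.3); two-sided threshold p ≤ 0.05 (6.5.2); Fisher (synopsis) and Wilcoxon rank-sum (6.5.2); a yes/no outcome per patient.

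**Step 1. Fisher, 4/10 v 0/10.** Given 4 events among 20 patients, the chance that all fall in one named arm is C(10,4)/C(20,4) = 210/4845 = 0.0433. The mirror result is equally extreme, so p = 2 × 0.0433 = 0.087.

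**Step 2. Asymptotic Wilcoxon, same table.** U = 4×10 + ½×6×10 = 70, against an expected 50. The tie-corrected variance is (10×10/12) × [21 − ((4³−4) + (16³−16))/(20×19)] = 8.333 × (21 − 4140/380) = 84.21, so the SD is 9.177. Then z = 20/9.177 = 2.179 and p = 0.029. With continuity correction, z = 19.5/9.177 = 2.125 and p = 0.034. A t approximation gives 0.042, or 0.047 with the correction. All four variants are below 0.05.

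**Step 3. Exact Wilcoxon.** With the total number of events fixed, U depends only on how many events fall in one arm. Its permutation distribution is the hypergeometric distribution that Fisher uses, and with equal arms the two-sided p-values coincide. Enumeration confirms that they are identical in every table.

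**Step 4. All tables.** There are 11 × 11 = 121 tables, or 11 × 12/2 = 66 after removing mirror images. Fisher and the asymptotic Wilcoxon disagree at 0.05 in 6 of the 66 (12 of 121 with mirror images):

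| Events per 10 | Fisher p | Wilcoxon p (with continuity correction) | Miettinen-Nurminen 95% CI for the difference, points |
|---|---|---|---|
| 4 v 0 | 0.087 | 0.029 (0.034) | 5.6 to 69.3 |
| 6 v 1 | 0.057 | 0.022 (0.025) | 7.6 to 77.6 |
| 7 v 2 | 0.070 | 0.029 (0.032) | 5.3 to 78.0 |
| 8 v 3 | 0.070 | 0.029 (0.032) | 5.3 to 78.0 |
| 9 v 4 | 0.057 | 0.022 (0.025) | 7.6 to 77.6 |
| 10 v 6 | 0.087 | 0.029 (0.034) | 5.6 to 69.3 |

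In each of these Wilcoxon is significant and Fisher is not; the reverse never occurs. The other 60 tables agree.

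**Step 5. How often.** The protocol gives no event rates, so these are assumptions. At equal true rates from 5% to 50%, the chance of a discordant table is at most about 3%. For assumed true differences it is 8.6% (10% v 30%), 18.9% (5% v 40%) and 23.7% (1% v 40%).

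**Step 6. The interval.** If the Miettinen interval is read as a Miettinen-Nurminen interval for the difference, it excludes 0 in the same six tables. On that reading, two rules within the synopsis can also disagree.

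**Step 7. Zero events in a primary endpoint.** The exact (Clopper-Pearson) 95% upper limit for 0/10 is 1 − 0.025^(1/10) = 0.308, or 30.8%. For 0/10 v 0/10, the Miettinen-Nurminen interval for the difference runs from −28.8 to +28.8 points.

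**The case against.** The strongest reply is that little depends on this. The trial is exploratory, the synopsis describes the analysis as mainly descriptive, section 6.5.1 is descriptive, and section 6.5.3 only counts events and subjects for MACE and SAEs. No stated decision rests on a categorical p-value. This stands, and it limits the severity. It does not remove the conflict, because 6.5.2 prescribes a comparison and a threshold for the secondary endpoints and the synopsis prescribes a different test.

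A second reply is that the rank-sum test is legitimate for binary data. That also stands: the exact form is Fisher's test. Even the asymptotic form kept its false-positive rate below 5% at the equal rates tried (4.2% at a rate of 50%, against 1.3% for Fisher). The fault is that two tests are named and the form of one is left open, not that Wilcoxon is invalid.

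A reader might infer more than the protocol supports:

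- *The two rules give opposite answers at this sample size.* They can, in 6 of 66 tables, and only if the asymptotic Wilcoxon is used. Section 6.5.2 does not say that it is.
- *The test conflict reaches the primary endpoints.* It does not. Section 6.5.2 covers secondary endpoints only.
- *The protocol plans no interval for the primary endpoints.* The synopsis promises 95% intervals for rates; 6.5.1 fails to repeat this.
- *The synopsis contradicts itself on Fisher and Miettinen.* That follows only if the interval is for a difference, which the synopsis does not say.

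**Conclusion.** The point holds in a limited form. Binary secondary endpoints, with MACE incidence the clearest example, have two stated tests. With 10 per arm and the asymptotic Wilcoxon, the choice changes the result at 0.05 in 6 of 66 distinct tables, always towards significance under Wilcoxon. With the exact Wilcoxon there is no difference. For the primary endpoints the problem is separate and smaller: 6.5.1 drops the interval that the synopsis promises, and the synopsis leaves its type unclear.

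The count of tables rests on complete data in 10 patients per arm. The probabilities of a discordant result rest on assumed event rates. The protocol should be corrected, but nothing here undermines the design.

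**What to change.** 1. In both the synopsis and 6.5.2, name Fisher's exact test as the only test for binary endpoints. Offering an alternative such as Boschloo's test would reopen the choice: for 4/10 v 0/10 it gives p = 0.033 against Fisher's 0.087.
2. Restrict the Wilcoxon rank-sum test to ordered scales such as NYHA class.
3. In 6.5.1, report each primary endpoint with an exact (Clopper-Pearson) 95% interval for each arm.
4. In the synopsis, say what the Miettinen interval is for. If a Miettinen-Nurminen interval is kept, label it as an interval for the between-group difference and present it descriptively, because it can exclude 0 where Fisher is not significant.

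The cost is wording only, with no change to patients, visits or sample size. The exact interval is somewhat wider than a score interval (upper limit for 0/10: 30.8% against 27.8%). Fisher is the more conservative test: against 0/10, the smallest split that reaches significance is 5/10 (p = 2 × 252/15504 = 0.033), where the asymptotic Wilcoxon would already reach it at 4/10.
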